- 12 Participants are required to undergo the ^{14}C UBT in the fasting state before breakfast during the screening period (Day -14 to Day -2), and the baseline period (Day -1), on Day 8 and Day 16 and during the follow-up period (Day 44 to Day 50).
- 13 After all examinations and PK blood collection are completed on Day 17, participants may be discharged from the study center.
- 14 Participants are required to return to the study center for follow-up visits from Day 44 to Day 50. Adverse events and laboratory abnormalities are followed up until the complete response or the return to baseline levels, the assessment of safety and tolerability is performed, and ^{14}C UBT is performed to evaluate the effect of Hp eradication.

Schedule of Activities for Group D

Study Procedures		Screening period	Baseline period	Hospitalization/Dosing period										Follow-up	
				D-14~D-2	D-1	D1	D2	D3	D4	D5	D6	D7	D8	D9	
Screening	Signing of ICF	X													
	Demographics	X													
	Medical and surgical history	X	X												
	Concomitant medications	X	X	X	X	X	X	X	X	X	X	X	X	X	X
	Chest plain X-ray ¹	X													
	Abdominal Doppler ultrasound ²	X													
	Infectious disease screening ³	X													
	Breath alcohol test		X												
	Urine drug screening ⁴		X												
	Serum pregnancy test ⁵	X	X											X	
Enrollment	Verification of inclusion and exclusion criteria	X	X												
	Admission		X												
Study treatment administration	Randomization		X												
	Dosing ⁶			X	X	X	X	X	X	X	X	X			
Safety and tolerability assessment	Clinical laboratory tests ⁷	X	X		X		X		X		X		X		X
	Physical examination ⁸	X	X				X		X		X		X		X
	12-lead ECG ⁹	X	X	X								X		X	
	Vital signs ¹⁰	X	X	X	X	X	X	X	X	X	X	X	X	X	

Study Procedures		Screening period	Baseline period	Hospitalization/Dosing period										Follow-up	
				D-14~D-2	D-1	D1	D2	D3	D4	D5	D6	D7	D8	D9	
	Recording of adverse events					X	X	X	X	X	X	X	X	X	X
PK sample collection	Blood sample ¹¹				X			X		X		X	X	X	
Hp eradication assessment	¹⁴ C UBT ¹²		X										X		X
End of study	Discharge ¹³													X	
	Follow-up, study completion ¹⁴														X

- 1 Results of chest plain X-ray within 1 year prior to screening are acceptable.
- 2 Abdominal Doppler ultrasound includes digestive system and urinary system, and the results within 1 month prior to screening are acceptable.
- 3 Infectious disease screening includes hepatitis B serologic test, hepatitis C antibody, HIV antigen/antibody, and treponema pallidum antibody tests (an additional rapid plasma regain (RPR) test is required in patients positive for treponema pallidum antibody), and the test results within 3 months prior to screening are acceptable.
- 4 Urine drug screening (morphine, and marijuana) is performed at baseline (Day -1).
- 5 The serum pregnancy test is performed only for female participants during the screening period (Day -14 to Day -2) and the baseline period (Day -1) and on Day 10.
- 6 Starting from Day 1, three oral doses are given each day for 7 consecutive days, at an interval of 8 h. The last dose is given in the morning of Day 8, and each participant receives 22 doses of the investigational product.
- 7 Clinical laboratory tests include hematology, urinalysis, blood biochemistry and coagulation function, which are carried out during the screening period (Day -14 to Day -2), and the baseline period (Day -1), before the first dose each on Day 2, Day 4 and Day 6, before the first dose on Day 8 and on Day 10 (48 h after dosing on Day 8). The test results obtained within 7 days of the screening period are acceptable for the baseline period, and no additional examination is required.
- 8 Physical examinations include skin, mucosa, lymph nodes, head, neck, chest, abdomen, and spine/limbs, which are carried out during the screening period (Day -14 to Day -2), and the baseline period (Day -1), and on Day 4, Day 6, Day 8 and Day 10.
- 9 The 12-lead ECG examination is performed during the screening period (Day -14 to Day -2), and the baseline period (Day -1), 2 h after the first dose on Day 1, within 60 min before dosing on Day 8 and 2 h and 48 h (Day 10) after the dosing.
- 10 Vital sign tests include blood pressure, pulse, body temperature and respiration, which are carried out during the screening period (Day -14 to Day -2), and the baseline period (Day -1), within 60 min before the first dose on Day 1 and 0.5, 2, 4, 8 and 12 h after the dosing, within 60 min before the first dose each from Day 2 to Day 7, within 60 min before dosing on Day 8 and 0.5, 2, 4, 8, 12, 24 h (Day 9) and 48 h (Day 10) after the dosing.
- 11 PK blood collection time: within 30 min before dosing on Day 1 and 0.5, 1, 1.5, 2, 2.5, 3, 3.5, 4, 5, 6, 7 and 8 h (before the second dose on the day) after the dosing, within 30 min before dosing each on Day 3, Day 5 and Day 7, within 30 min before dosing on Day 8 and 0.5, 1, 1.5, 2, 2.5, 3, 3.5, 4, 5, 6, 7, 8, 9, 10, 11, 12, 24 h (Day 9) and 48 h (Day 10) after the dosing.
- 12 Participants are required to undergo the ¹⁴C UBT in the fasting state before breakfast during the screening period (Day -14 to Day -2), and the baseline period (Day -1), on Day 8 and during the follow-up period (Day 37 to Day 43).
- 13 After all examinations and PK blood collection are completed on Day 10, participants may be discharged from the study center.

14 Participants are required to return to the study center for follow-up visits from Day 37 to Day 43. Adverse events and laboratory abnormalities are followed up until the complete response or the return to baseline levels, the assessment of safety and tolerability is performed, and ¹⁴C UBT is performed to evaluate the effect of Hp eradication.

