Exclusion Criteria	
Participants were not to be enrolled if they met any of the following exclusion criteria:
 
 1 History of helicobacter pylori eradication therapy (including participation in other clinical studys for helicobacter pylori eradication); 2 Those who smoked more than 5 cigarettes per day in the 3 months prior to screening; 3 Those who are allergic to the investigational product or or its excipients, or participants with allergic constitution (multiple drug and food allergies); 4 Those who have a history of drug and/or alcohol abuse (average weekly consumption of ≥ 14 units of alcohol: 1 unit = 285 mL of beer, or 25 mL of spirits, or 100 mL of wine); 5 Those who have blood donation or massive blood loss (> 450 mL) within 3 months prior to screening; 6 Those who have taken any drug that changes the activity of liver enzyme within 28 days prior to screening; 7 Those who have taken any prescription drugs, over-the-counter drugs, any vitamin products, or herbal remedies within 14 days prior to screening; 8 Those who have taken special diet (including pitaya, mango, grapefruit, etc.) or have had strenuous exercise within 2 weeks prior to screening, or other factors affecting drug absorption, distribution, metabolism, excretion, etc.; 9 Those who have had a major change in diet or exercise habits recently; 10 Those who have taken the other study drug or participated in the other clinical study that have not been finished within 1 month prior to administration of the investigational products; 11 Those who have a history of dysphagia or any gastrointestinal disease affecting drug absorption; 12 Those who have any disease that increases the risk of bleeding, such as hemorrhoids, acute gastritis or gastric and duodenal ulcers; 13 Those who have abnormal ECG with clinical significance; 14 Female participants who are in lactation or have a positive result in serum pregnancy test at screening or during the course of the study; 15 Those with symptoms of cardiovascular, digestive, respiratory, urinary, neurological, hematological, immunological, endocrine system or tumor, and mental illness or with past medical history that has not been cured; 16 The following diseases (including but not limited to gastrointestinal, renal, hepatic, neurologic, hematologic, endocrine, oncologic, pulmonary, immunologic, psychiatric or cardiovascular and cerebrovascular diseases) with clinically significant abnormalities in clinical laboratory tests or other clinical findings;

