
	
17 Viral hepatitis (including hepatitis B and C), HIV antibody, treponema pallidum antibody positive (those with positive treponema pallidum antibody need additional RPR test);
 
18 Acute illness or concomitant medication from the time of signing the informed consent form to the time before administration of investigational product;
 
19 Consumption of chocolate, any caffeine-containing or xanthine-rich food or beverages within 48 hours prior to administration of the investigational product;
 
20 Those who have taken any alcohol-containing products within 48 hours prior to administration of the investigational product;
 
21 Those with a positive result in urine drug screening or a history of drug abuse or drug use within the past 5 years;
 
22 Other conditions considered by the investigator unsuitable for participation in the study.

Safety and Tolerability Judgement Criteria	CTCAE 5.0 criteria are used.
Safety and Tolerability Evaluation	
All participants are observed for any adverse events occurring during the clinical study, and their clinical manifestations, severity, onset time, end time, treatment measures and outcome are recorded, and their correlation with the investigational product shall be determined.
 
Safety and tolerability evaluation mainly includes adverse events (AE), physical examination, vital signs (blood pressure, pulse rate, respiratory rate and body temperature), clinical laboratory tests (hematology, urinalysis, blood biochemistry, coagulation function) and ECG.

Concomitant Medications	
All non-investigational products taken by the participant from the time of signing the informed consent form through the last study visit are considered concomitant medications, and information regarding the medication will be recorded on the CRF, including the drug name (trade name and generic name), start date, dose, mode of administration, reason for use, and stop date.
 
Use of concomitant medications should be minimized during the study. However, if these medications are beneficial to the participant and necessary, and are not likely to interfere with the study, they may be administered at the discretion of the investigator.

Prohibited Medications	Any prescribed drugs or over-the-counter drugs, including vitamins, minerals, nutritional supplements, herbal remedies, etc., are not allowed within 2 weeks prior to screening and during the study, except for drugs used to treat adverse events.

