Statistical Analysis	
Definition of Statistical Analysis Set:
 
 • Full Analysis Set (FAS): Refers to the participant of all randomized participants who have taken the investigational product at least once; • Modified Intent-to-Treat Analysis Set (mITT): Refers to all randomized participants who have ¹⁴C UBT performed on Day 28 to 34 after the last dose of the study; • Per Protocol Set (PP): Refers to participants without major protocol violation: participants who are randomized and receive more than 80% (inclusive) of the expected total amount of investigational product, and undergo ¹⁴C UBT on Day 28 to 34 after the last dose of the study; • Safety Analysis Set (SS): refers to the participant participant who entered the study and used the investigational product at least once; • Pharmacokinetic Concentration Analysis Set (PKCS): refers to all enrolled participants who have used the investigational product and have at least one observed PK concentration data; • Pharmacokinetic Parameter Analysis Set (PKPS): refers to all enrolled participants who have used the investigational product and have at least one observed PK parameter data. 
Demographic Analysis: Demographic analyses are based on the Full Analysis Set (FAS). Descriptive statistics will be performed for all demographics (age, gender, weight, height, BMI, ethnicity, etc.) and baseline characteristics, taking the last valid measurement data before the administration of the investigational product as the baseline.
 
Analysis of Helicobacter pylori eradication effect: The eradication effect will be analyzed descriptively by frequency (percentage) according to four ¹⁴C UBT results (negative or positive) at baseline, Day 8, Day 16, and Day 44 to 50 of follow-up in Group A, Group B, Group C and the Control Group, and three ¹⁴C UBT results (negative or positive) at baseline, Day 8, and Day 37 to 43 of follow-up in Group D, based on the full analysis set (FAS). And make inter-group comparison, which shall focus on comparison between the test group and the control group, supplemented by the comparison among the test groups. Inter-group comparison of percentages will adopt Fisher's exact test. H. pylori eradication rate is defined as the proportion of participants with negative ¹⁴C UBT results from Day 28 to Day 34 after the last dose of the study. At the same time, the H. pylori eradication rate of each group will be calculated in the mITT analysis set and the PP analysis set, and the sensitivity analysis will be performed. There are no clear statistical hypotheses in this study and all statistical tests are exploratory test with a two-sided 5% nominal significance level. The statistical analysis method and plan are detailed in the statistical analysis plan.

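### Does the plan need a stated rule for a negative final breath test after a non-study antibacterial?

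*Combined protocol and SAP*

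**What the plan says.** The Statistical Analysis row of the synopsis states that the H. pylori "eradication rate is defined as the proportion of participants with negative" UBT results in the window 28 to 34 days after the last dose. The main analysis uses the FAS (randomized, at least one dose), repeated in mITT (randomized, with a final UBT) and in PP. PP "Refers to participants without major protocol violation: participants who are randomized and receive more than 80% (inclusive) of the expected total amount" of study drug, and it also requires the final UBT. None of these definitions mentions other drugs. The same row calls all tests exploratory, at a nominal two-sided 5% level, and leaves detailed methods to the SAP.

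Rules on other drugs appear in four places:

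- **Exclusion criterion 7** bars entry to "Those who have taken any prescription drugs, over-the-counter drugs, any vitamin products, or herbal remedies within 14 days prior to screening".
- **Exclusion criterion 18** bars "Acute illness or concomitant medication from the time of signing the informed consent form to the time before administration of investigational product".
- **Prohibited Medications**: other drugs "are not allowed within 2 weeks prior to screening and during the study, except for drugs used to treat adverse events".
- **Concomitant Medications**: necessary drugs are tolerated if they "are not likely to interfere with the study, they may be administered at the discretion of the investigator".

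On recording, the Concomitant Medications row says that non-study products taken "from the time of signing the informed consent form through the last study visit are considered concomitant medications" and go on the CRF with name, dates, dose and reason. For adverse events, the Safety and Tolerability Evaluation row adds that "treatment measures and outcome are recorded".

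**The concern.** Amoxicillin is part of the study's own regimens. It is a fair inference, though the documents do not state it, that a non-study antibacterial could turn a UBT negative. If so, the assigned regimen would be credited with an effect that may not be its own. The entry tests are guarded by criteria 7 and 18, while the endpoint test has no matching analysis rule. PP may not help, because a major violation is not defined for medication and the adverse-event exception makes some use permissible.

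Detection also looked doubtful. Participants are outpatients between discharge and the final UBT. The Follow-up Period row and footnote 14 of both schedules list adverse events, laboratory abnormalities, safety assessment and UBT, but no medication check. The concomitant-medication row for Groups A, B, C and Control shows no mark at D44–D50. At stake are the eradication rates in groups of 10 or 20, where each participant counts for a lot.

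**Working it through.** **1. Which sets would count the participant?** Take a participant with full dosing, an antibacterial for an adverse event after discharge, and a negative final UBT.

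| Set | Condition on other drugs | Result |
|---|---|---|
| FAS | none | counted as eradicated |
| mITT | none | counted as eradicated |
| PP | only through an undefined major violation | open |

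The PP answer depends on how two rows are read together. Under the adverse-event exception the use is permitted. Under the condition in the Concomitant Medications row, a drug thought able to alter the UBT is hard to call unlikely to interfere. A blinded data review or the SAP would normally settle this.

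**2. Is the endpoint test unguarded?** No. Criteria 7 and 18 are rules of conduct, and the endpoint test has one too: the prohibition during the study. What is missing is an analysis rule, and the entry tests have none either.

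**3. Would the use be known?**

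- Outpatient interval, Groups A, B, C and Control: 44 − 17 = 27 to 50 − 17 = 33 days. Group D: 37 − 10 = 27 to 43 − 10 = 33 days. This is the only outpatient interval after dosing starts; screening is also outpatient.
- The recording rule runs to the last visit in every group. The follow-up text does not repeat it, but does not contradict it. Drugs for adverse events have a second record.
- Schedule for A, B, C and Control: the medication row has 19 marks for 20 columns (2 + 17 + 1). The vital-signs row also has 19 and agrees with its footnote, so the blank may be real. But the table as read has 16 dosing marks for 15 dosing days, and the last ECG mark falls under D44–D50 although footnote 9 puts it on D17.
- Schedule for Group D: the medication row has 14 marks, but there are only 2 + 10 + 1 = 13 visits. The laboratory row has 8 marks against 7 visits in its footnote, and the physical-examination row 7 against 6. This table is not evidence either way.

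**4. Size.** The stated group sizes reproduce: 80 × (2, 2, 1, 1, 2)/8 = 20, 20, 10, 10, 20. The documents give no expected rates, so the counts below are assumed.

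- FAS, one negative recoded as not eradicated: 1/20 = 5 points; 1/10 = 10 points.
- PP, one negative removed: x/n − (x − 1)/(n − 1) = (n − x)/(n(n − 1)).
  - n = 20: x = 18 gives 2/380 = 0.5 points; x = 10 gives 10/380 = 2.6 points.
  - n = 10: x = 9 gives 1/90 = 1.1 points; x = 5 gives 5/90 = 5.6 points.
- Width of the exact (Clopper–Pearson) 95% interval: 18/20, 30.5 points; 10/20, 45.6; 9/10, 44.2; 5/10, 62.6.

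One participant therefore shifts a rate by far less than the width of its own interval.

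**The case for a change.** The best case for a change is that it is cheap and that rules are better set before the data are seen. In groups this small, one recode can cross the nominal 5% level. With Fisher's exact test, 17/20 against 10/20 gives p = 0.041, and 16/20 against 10/20 gives p = 0.096. For n = 10, 9/10 against 10/20 gives p = 0.049, and 8/10 gives p = 0.235. Nor need use be rare: the chance of at least one user among 80, 1 − (1 − q)^80, is 55% at an assumed q of 1% and 98% at 5%.

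Part of this stands. The text states no handling rule, and the follow-up text does not repeat the recording duty. The rest carries less weight:

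- The p-value examples start from counts chosen just below 0.05, in a study that states no hypotheses.
- A recoded Control participant moves p the other way (17/20 against 9/20, p = 0.019), so the direction of bias is not fixed.
- A user biases a rate only if the final UBT would otherwise have been positive. The chance of such a case is below the chance of a user, and nothing in the documents lets one estimate it.
- Counting every user as a failure would misclassify some true eradications, more so in a group with more treated adverse events.

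**Conclusion.** No change to the plan follows. The missing item is a handling detail that analysts can fill from data the protocol already requires: drug name, dates and reason, through the last visit. They can list users by group, decide PP status case by case before the analysis and, if any users exist, check the rate with them counted as not eradicated. None of this alters the primary FAS rate. The silence of the follow-up text and the blank schedule cell are at most clerical beside an explicit recording rule, and the cell may be an artefact of reading the table.

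The effect is 5 or 10 points per recoded participant in FAS, and 0.5 to 2.6 points (n = 20) or 1.1 to 5.6 points (n = 10) if one is removed from PP. Exact intervals over the same assumed counts are at least 30 points wide. The conclusion assumes that the Concomitant Medications row is followed at the final visit and that the results are read as exploratory. Which drugs may be given is a clinical matter and is not addressed here.

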Study Endpoints	
Primary Study Endpoint H. pylori eradication rate (confirmed by ^{14}C UBT) on Days 28 to 34 after the last dose.
 
Secondary Study Endpoints
 
 1 The negative rate of ^{14}C UBT on Day 8 after the first dose; 2 The negative rate of ^{14}C UBT on Day 16 after the first dose; 3 Safety endpoints: Incidence of adverse events (AE) during the study, correlation with the investigational medicinal product and severity, laboratory tests, vital signs, ECG, physical examination, etc.; 4 Pharmacokinetic endpoints: Pharmacokinetic parameters of TNP-2198, rabeprazole, amoxicillin in each group of consecutive administrations.
Protocol No.	TNP-2198-PO-06
Sponsor	TenNor Therapeutics
Clinical Trial Notification No.	CXHL1800160/161
Study Facility	Phase I Drug Clinical Study Center of the First Hospital of Jilin University, Department of Gastroenterology of the First Hospital of Jilin University
Study Phase	Phase Ic/IIb

Investigational Products	
TNP-2198 capsules
 
 • Manufacturer: WuXi STA (Shanghai) Co., Ltd. (entrusted) • Strength: 100 mg • Storage Condition: Preserve in tightly closed containers, protected from light and stored at ambient temperature (10-30 °C) 
Rabeprazole Sodium Enteric-coated Tablets
 
 • Manufacturer: Eisai China Inc. • Drug Approval No.: GuoYaoZhunZi H20090090 • Strength: 20 mg • Storage Condition: Preserve in tightly closed containers, protected from light and stored below 25 °C 
Amoxicillin Capsules
 
 • Manufacturer: Zhuhai United Laboratories (Zhongshan) Co., Ltd. • Drug approval No.: GuoYaoZhunZi H44021351 • Strength: 0.5 g • Storage conditions: to be determined 												

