	
The participants take the investigational product every day on Days 1 to 14 (D1-D14) and take the last dose of the investigational product in the morning of Day 15 (D15) according to the dosage regimen of each group. Pharmacokinetic blood samples will be collected at the time points scheduled in the protocol during the study, and safety and tolerability evaluation, and ¹⁴C UBT will be conducted. All participants are discharged from the study center after safety and tolerability evaluation and PK blood collection are completed on Day 17 (D17), and return to the study center for follow-up visit on Days 44 to 50 (D44-D50). Adverse events and laboratory test abnormalities are followed until complete response or return to baseline or steady state, safety and tolerability assessments are performed, and ¹⁴C UBT is performed to evaluate the effect of Hp eradication.
 
Study procedures of Group D (administration for 7 consecutive days):
 
The investigational product is administered daily on study Days 1 to 7 (D1-D7), and the last dose of the investigational product is administered as specified in the dosage regimen in the morning of Day 8 (D8). Pharmacokinetic blood samples will be collected at the time points scheduled in the protocol during the study, and safety and tolerability evaluation, and ¹⁴C UBT will be conducted. All participants are discharged from the study center after safety and tolerability evaluation and PK blood collection are completed on Day 10 (D10), and return to the study center for follow-up visit on Days 37 to 43 (D37-D43). Adverse events and laboratory test abnormalities are followed until complete response or return to baseline or steady state, safety and tolerability assessments are performed, and ¹⁴C UBT is performed to evaluate the effect of Hp eradication.

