	
The hospitalization/administration period is from D1 to D17. According to the dosage regimen, the investigational product is orally administered on time every day for 14 consecutive days, and the last dose of the investigational product is administered in the morning of D15. Physical examination, vital signs, blood routine, urine routine, blood biochemistry, coagulation function, ECG, ¹⁴C UBT and other tests will be performed during hospitalization, and PK blood samples will be collected at the time points specified in the protocol. After all tests (serum pregnancy test is required only for female participants) and PK blood collection are completed on D17, the participants can be discharged from the study center.
 
2) Group D
 
The hospitalization/administration period is from D1 to D10. According to the dosage regimen, the investigational product is orally administered on time every day for 7 consecutive days, and the last dose of investigational product is administered in the morning of D8. Physical examination, vital signs, blood routine, urine routine, blood biochemistry, coagulation function, ECG, ¹⁴C UBT and other tests will be performed during hospitalization, and PK blood samples will be collected at the time points specified in the protocol. Participants can be discharged from the study center on D10 after completion of all tests (serum pregnancy test for female participants only) and PK blood sampling.
																																							
Follow-up Period	
Participants in Group A, Group B, Group C and Control Group will return to the study center for follow-up visit from D44 to D50. Participants in Group D will return to the study center for follow-up visit from D37 to D43. Adverse events and laboratory test abnormalities are followed until complete response or return to baseline or steady state, safety and tolerability assessments are performed, and ¹⁴C UBT is performed to evaluate the effect of Hp eradication.
																																							

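### The follow-up UBT is scheduled by study day, but the endpoint, eradication rate, mITT and PP count from the last dose, so some tested early stoppers can fall outside them on timing alone

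*Combined protocol and SAP*

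**What the plan says.** Four definitions are anchored to the last dose:

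- Study Endpoints places the primary UBT "on Days 28 to 34 after the last dose".
- Statistical Analysis admits to mITT randomized participants with a "UBT performed on Day 28 to 34 after the last dose of the study".
- PP has the same UBT condition, and participants must also "receive more than 80% (inclusive) of the expected total amount of investigational product".
- The eradication rate is the proportion with negative "UBT results from Day 28 to Day 34 after the last dose of the study".

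The test itself is anchored to the study day. The Follow-up Period entry says, for the 14-day regimens, "Participants in Group A, Group B, Group C and Control Group will return to the study center for follow-up visit from D44 to D50". For the 7-day regimen it says "Participants in Group D will return to the study center for follow-up visit from D37 to D43". Study Design, Evaluation of Helicobacter Pylori Eradication and both Schedules of Activities agree. The planned last dose is the morning of D15, or of D8 in Group D.

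The paragraph on analysis of the eradication effect uses both anchors. It tabulates FAS results by visit, including "Day 44 to 50 of follow-up in Group A, Group B, Group C and the Control Group" and the D37-D43 visit for Group D, and then defines the eradication rate by days since the last dose. The text provided does not move the visit for a participant who stops early, and gives no rule for a UBT outside the window.

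**The concern.** The two anchors agree, at best, only for participants who finish treatment. Each day of earlier stopping adds a day between the last dose and a visit that does not move, until no permitted visit day is within 34 days.

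Read literally, such a participant attends, is tested and has a result, but is outside mITT and cannot be counted as eradicated even if negative. In the FAS the same negative test counts in the display by visit and not in the eradication rate. A UBT in the window is the only condition for entering mITT beyond randomization, so the timing rule alone decides who is in it. If participants stop because they tolerate a regimen poorly, exclusion is related to treatment. The stopping days affected also differ between the 14-day groups and Group D.

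**Working it through.** **Inputs.** Planned last dose D15 (Groups A, B, C, Control) or D8 (Group D); visit D44-D50 or D37-D43; window 28-34 days; planned doses 29 (A, B, Control), 43 (C) and 22 (D); group sizes 20/20/10/10/20. All are in the synopsis.

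**Step 1: the plan's own window, for completers.** Gap = visit day − last-dose day.
- 14-day groups: 44 − 15 = 29 to 50 − 15 = 35.
- Group D: 37 − 8 = 29 to 43 − 8 = 35.

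Elapsed days therefore give 29-35, not 28-34. Calling the last-dose day Day 1, as the secondary endpoints do when Day 8 after the first dose is study day D8, gives 30-36. Counting only the full days between last dose and test gives exactly 28-34 in both schedules, but no section states that convention.

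**Step 2: early stoppers, elapsed days.** For last-dose day L the gap runs from 44 − L to 50 − L (Group D: 37 − L to 43 − L). The table counts visit days with a gap of 28-34.

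| Last dose, 14-day groups | Gap (days) | Visit days in window | Same gap in Group D: last dose |
|---|---|---|---|
| D15 (planned) | 29-35 | 6 of 7 | D8 (planned) |
| D14 | 30-36 | 5 | D7 |
| D13 | 31-37 | 4 | D6 |
| D12 | 32-38 | 3 | D5 |
| D11 | 33-39 | 2 | D4 |
| D10 | 34-40 | 1 | D3 |
| D9 or earlier | 35 or more | 0 | D2 or earlier |

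So 9 of 15 possible last-dose days in the 14-day groups, and 2 of 8 in Group D, leave no qualifying visit day.

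**Step 3: other day counts.** With the last-dose day as Day 1, the cut-off for no qualifying day is D10 or earlier (Group D: D3 or earlier). With full days between, it is D8 or earlier (Group D: D1). The cut-off shifts, but the problem remains.

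**Step 4: the PP dose rule.** 80% of 29 is 23.2, so 24 doses are needed (24/29 = 82.8%), reached with the second dose of D12. 80% of 43 is 34.4, so 35 doses, also reached on D12. 80% of 22 is 17.6, so 18 doses, reached on D6. With no missed doses, an early stopper who meets the dose rule stopped on D12-D14 (Group D: D6-D7) and has 3 to 5 visit days in window (Group D: 4 to 5). Such a participant can still lose PP membership on timing.

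**Step 5: size.** One participant is 1/20 = 5 points or 1/10 = 10 points. The documents give no stopping rate and no expected eradication rates, so all counts below are assumptions. P-values are two-sided Fisher.

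*Example 1.* A group of 20 has 18 completers tested in window, 17 of them negative, and 2 stoppers at or before D9. Control is 12/20.
- Both stoppers positive: FAS 17/20 = 85% (p = 0.155); mITT 17/18 = 94% (p = 0.021).
- Both negative: FAS 17/20 = 85% by the last-dose rule (p = 0.155), or 19/20 = 95% by visit (p = 0.020).

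*Example 2.* 16 of 20 are negative at the visit against 8/20 in control, and k of the 16 are out of window.

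| k | FAS by last-dose rule | p | mITT | p |
|---|---|---|---|---|
| 0 | 16/20 = 80% | 0.023 | 16/20 = 80% | 0.023 |
| 1 | 15/20 = 75% | 0.054 | 15/19 = 79% | 0.023 |
| 2 | 14/20 = 70% | 0.111 | 14/18 = 78% | 0.025 |
| 3 | 13/20 = 65% | 0.205 | 13/17 = 76% | 0.045 |

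The mITT rate rises if those excluded are positive and falls if they are negative.

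**The case against.** The best reply is that the last dose of the study means the scheduled dose. The synopsis repeatedly treats the last dose as a fixed event on D15 or D8, names the D44-D50 or D37-D43 UBT as the test of eradication, and reaches exactly 28-34 if full days between are counted. On that reading nobody tested at the visit is lost and the FAS gives one rate. This is plausible and may be what was intended. But the text does not say so, and Study Endpoints says only the last dose.

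Three limits on reach also stand. Dosing is inpatient, no stopping rate is given, and nothing shows how many early stoppers would still attend follow-up. The eradication analysis rests on FAS, with mITT and PP used for sensitivity analysis. There are no formal hypotheses, so a p-value crossing 0.05 decides nothing.

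The text provided is a synopsis that refers detail to a statistical analysis plan. A rule for out-of-window tests may be there, but none appears here.

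A reader might infer more than the documents support:
- That every early stopper is dropped. Those stopping on D10-D14 (Group D: D3-D7) can be in window, depending on visit day.
- That mITT was designed to restore non-adherent participants and nearly repeats PP. No section states that purpose, and D10-D11 stoppers tested in window would be in mITT while failing the PP dose rule.
- That mITT will favour a poorly tolerated regimen. That depends on the results of those excluded, as the examples show.

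**Conclusion.** The concern holds as an unreconciled pair of anchors. If the last dose is the actual one and days are elapsed days, a tested participant whose last dose was on D9 or earlier (Group D: D2 or earlier) is always outside mITT and PP and cannot meet the eradication-rate definition. Later stoppers depend on the visit day. On that reading, one paragraph gives two FAS answers for the same negative test. The cut-off moves by a day either way with the counting convention, and the problem disappears only if the scheduled last dose was meant.

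The effect on the results cannot be estimated, and it may be nil if nobody stops early. With groups of 10 to 20, one participant is enough to move a rate by 5 to 10 points, and the exclusion may be related to tolerability. The definitions should be corrected before the data are analysed. The documents do not show that the trial's conclusions will be biased.

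**What to change.** For all participants, define the primary endpoint, the eradication rate, and the UBT condition for mITT and PP by the UBT at the scheduled follow-up visit (D44-D50; Group D D37-D43), whatever the actual last-dose day. Leave exclusion of early stoppers from PP to the 80% dose rule. Use the same result in the FAS display by visit and in the eradication rate.

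The elapsed gap is then at least 29 days for completers (44 − 15; 37 − 8) and 30 for early stoppers (44 − 14; 37 − 7), so no test at the visit is earlier than the present 28-day minimum. The rule should cover everyone. If it covered early stoppers only, a completer tested on D50, or D43 in Group D, would stay outside the window at 35 elapsed days.

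The cost is a change of wording in the endpoint and analysis-set definitions, with no added visit or test. The downside is small: early stoppers are tested up to 49 days after their last dose (50 − 1), against 35 at most for completers, and the mITT rate may be slightly lower.
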